## **Description of Subject Population**

### **Sample #1**

Specify subject population

Adults with AUD

Number of completers required to accomplish study aims

10

Projected number of subjects who will be enrolled to obtain required number of completers

20

Age range of subject population

18-65

Gender, Racial and Ethnic Breakdown

We plan to enroll 20 participants into the study. Both males and females will be recruited. All eligible participants are accepted; however, past experience with recruitment at STARS suggests that the approximate gender distribution for this study will likely be 20% female and 80% male. Previous and ongoing studies at STARS have had samples comprised of approximately 50% Caucasians, and 50% ethnic minorities distributed as 24% African-American and 22% Hispanic-American, and 4% other. We anticipate a similar representation in this project. We will make every effort to recruit minority patients in order to ensure the generalizability of our findings to the overall treatment population.

Description of subject population

We plan to enroll 20 participants into the study who meet criteria for current AUD.

## **Recruitment Procedures**

Describe settings where recruitment will occur

All screening and study procedures will occur at the Substance Treatment and Research Services (STARS) of the Division on Substance Abuse (STARS Downtown) situated on [name]

How and by whom will subjects be approached and/or recruited?

Screening for this study will be covered by the Substance Treatment and Research Service (STARS) umbrella screening protocol #6582R (PI: [name]). Trained research assistants and administrative assistants under the supervision of the principal investigator conduct the initial phone screening. Under protocol #6582R, patients who contact STARS interested in research trial participation are informed that they will be asked questions of a personal nature and asked to provide verbal consent for such questions. A "phone screen" form is completed by the phone screener, which asks basic demographic

---

information, contact information (for scheduling purposes) and description of substance use to determine whether an in-person evaluation appointment is appropriate. Individuals are also informed that if they make an initial screening appointment this "phone screen" information will be forwarded to the clinician to facilitate the first meeting.

All patients will receive an explanation of the study risks, benefits, treatments, procedures, and option for alternative treatments. Patients who wish to participate will be asked to sign the treatment consent form following resolution of any questions and clear indication that they understand the nature of the study and consent form.

How will the study be advertised/publicized?

We will recruit individuals with AUD through newspapers, radio and public service announcements coordinated by the NYSPI Public Relations Office. This method has proven successful in several clinical trials at STARS. All advertisements will be sent to the Institutional Review Board for approval. The first phase of recruitment is a structured telephone interview when the initial contact is made. Individuals interested in receiving treatment for AUD will be asked to come to STARS for additional screening as per protocol #6582R. Those patients who meet criteria for AUD and all other inclusion/exclusion criteria will be asked if they are interested in participating in the study.

Do you have ads/recruitment material requiring review at this time?

No

Does this study involve a clinical trial?

Yes

YOU MUST REGISTER AT [ClinicalTrials.gov](https://ClinicalTrials.gov) IMMEDIATELY UPON RECEIPT OF IRB APPROVAL AND **PRIOR TO ENROLLMENT** OF THE FIRST SUBJECT. YOU WILL BE PROVIDED WITH A NCT REGISTRATION NUMBER ON REGISTRATION. PLEASE REVISE THIS SECTION OF THE PROTOCOL SUMMARY FORM TO INCLUDE THE NCT NUMBER AND RE-SUBMIT AS AN AMENDMENT TO THE IRB.

## Concurrent Research Studies

Will subjects in this study participate in or be recruited from other studies?

Yes

Describe concurrent research involvement

Screening for this study will be covered by the Substance Treatment and Research Service (STARS) umbrella screening protocol #6582R (PI: [name]). Trained research assistants and administrative assistants under the supervision of the principal investigator conduct the initial phone screening. Under protocol #6582R, patients who contact STARS interested in research trial participation are informed that they will be asked questions of a personal nature and asked to provide verbal consent for such questions. A "phone screen" form is completed by the phone screener, which asks basic demographic information, contact information (for scheduling purposes) and description of substance use to determine whether an in-person evaluation appointment is appropriate. Individuals are also informed that if they make an initial screening appointment this "phone screen" information will be forwarded to the clinician to facilitate the first meeting.

## **Inclusion/Exclusion Criteria**

Name the subject group/sub sample

Adults with AUD

Create or insert table to describe the inclusion criteria and methods to ascertain them

1. Meets DSM-5 criteria for current alcohol use disorder	MINI International Neuropsychiatric Interview for DSM-5; psychiatric evaluation
2. Reports drinking a minimum of 5 standard drinks for men or 4 standard drinks for women at least 4 days per week over the past 28 days	Self-report
3. Between the ages of 18 and 65	Demographics
4. Able to provide informed consent and comply with study procedures	MD assessment

Create or insert table to describe the exclusion criteria and methods to ascertain them

1. Subjects with any current psychiatric disorder as defined by DSM-5, other than AUD, that in the investigator's judgment might require intervention over the course of the study.	MINI International Neuropsychiatric Interview for DSM-5; psychiatric evaluation
2. Subjects receiving psychotropic medication treatment	Medical history; psychiatric evaluation
3. Evidence of moderate-to-severe alcohol withdrawal (CIWA-Ar $\geq 13$ )	Medical evaluation
4. History of alcohol withdrawal seizures or alcohol withdrawal delirium	Medical history
5. History of allergic reaction to candidate medication (pregabalin)	Medical history
6. Pregnancy, lactation, or failure in females patients to use adequate contraceptive methods	Medical history; serum HCG
7. Unstable physical disorders which might make participation hazardous	Medical history; physical examination; ECG; laboratory testing
8. Subjects who have a current DSM-5 diagnosis of moderate or severe substance use disorder, with the exception of alcohol, nicotine and caffeine use disorders. A diagnosis of a mild substance use disorder will not be exclusionary, as long as the current primary substance use disorder is alcohol.	MINI International Neuropsychiatric Interview for DSM-5; psychiatric evaluation; urine toxicology
9. Are legally mandated to participate in alcohol use disorder treatment program	Self-report
10. Cognitively impaired	psychiatric interview; MMSE will be completed on all

individuals over 60  
years old

## **Waiver of Consent/Authorization**

Indicate if you are requesting any of the following consent waivers

Waiver of consent for use of records that include protected health information (a HIPAA waiver of Authorization)

No

Waiver or alteration of consent

No

Waiver of documentation of consent

No

Waiver of parental consent

No

## **Consent Procedures**

Is eligibility screening for this study conducted under a different IRB protocol?

Yes

Indicate NYSPI IRB #

6582R

Describe Study Consent Procedures

Screening for this study will be covered by the Substance Treatment and Research Service (STARS) umbrella screening protocol #6582R (PI: [name]). Trained research assistants and administrative assistants under the supervision of the principal investigator conduct the initial phone screening. Under protocol #6582R, patients who contact STARS interested in research trial participation are informed that they will be asked questions of a personal nature and asked to provide verbal consent for such questions. A "phone screen" form is completed by the phone screener, which asks basic demographic information, contact information (for scheduling purposes) and description of substance use to determine whether an in-person evaluation appointment is appropriate. Individuals are also informed that if they make an initial screening appointment this "phone screen" information will be forwarded to the clinician to facilitate the first meeting.

Indicate which of the following are employed as a part of screening or main study consent procedures

Consent Form

## Study Procedures

Describe the procedures required for this study

*Study Participants:* Participants will be 20 men and nonpregnant women with AUD who report drinking a minimum of 5 standard drinks for men or 4 standard drinks for women at least 4 days per week over the past 28 days. The daily minimum drinking requirements are consistent with the commonly accepted definition of “binge drinking.” A minimum requirement of having a heavy drinking episode 4 days a week would select for a population of individuals who are drinking excessively more days than not. An exclusion threshold CIWA-Ar score of  $\geq 13$  is set to balance the need to protect participants from the consequences of untreated severe alcohol withdrawal symptoms and the need for the enrolled patients to have alcohol withdrawal symptoms of sufficient severity to detect between group differences. During the first two weeks of the study participants will be monitored frequently for the development of severe alcohol withdrawal symptoms. The gabapentin pilot study used an exclusion cut-off of CIWA-Ar score of  $\geq 13$  and there were no serious adverse events and no participants were removed from the trial due to the development of alcohol withdrawal, suggesting that a CIWA-Ar eligibility and drop-out threshold  $\geq 13$  combined with careful monitoring will appropriately protect participants from the risk of untreated alcohol withdrawal symptoms.

**Design Overview:** In a 9-week open label outpatient pilot trial, the ideal dosing, tolerability, and safety of pregabalin will be tested in 20 outpatients with AUD. The specific aims of the project are to determine in AUD outpatients 1) Pregabalin will be well tolerated and safe when used as an abstinence-initiation agent in AUD outpatients in doses ranging up to 600 mg per day. 2) the ideal target dose range and tolerability of pregabalin pharmacotherapy. Secondary outcome measures will be the end-of-study proportion of heavy drinking days and percent days abstinent compared to baseline. Exploratory measures include: 1) alcohol use as measured by secondary outcomes such as amount of drinks per day; and 2) the symptoms of alcohol withdrawal.

**Medication:** Pregabalin will be prepared by our pharmacy at the NY SPI. Pregabalin will be administered in 75 mg and 100 capsules. Pregabalin will be titrated over a 3-week period to the FDA maximum (600 mg per

---

**Assessment of Side Effects and Medication Compliance:** The research nurse and psychiatrist will query about side effects related to the study medication. Reported side effects and other treatment emergent events since the past visit will be recorded; additionally, the severity of the side effect/treatment emergent event, the action taken, and the continuation or resolution of the side effect/treatment emergent event will be documented.

**Medication Adherence Enhancement:** We will use a timeline followback interview and pill count with a weekly financial incentive (\$10) for medication bottle return to both enhance and measure medication adherence. Our prior studies have found a 91% rate of bottle return using this method. Participants are not provided reinforcement for ingesting medication—payment is tied solely to the return of the medication bottle. We considered serum blood levels and riboflavin over-encapsulation and fluorometric quantification, but decided those interventions were not cost-effective given the limited budget of this open-label investigation.

**Medical Management Treatment:** All participants will have a weekly supportive behavioral treatment session with the research psychiatrist using a manual designed for pharmacotherapy trials in subjects with alcohol use disorders (Pettinati et al. 2005). This psychosocial intervention facilitates compliance with study medication and other study procedures, promotes abstinence from marijuana and other substances,

---

and encourages mutual-support group attendance. [name] will provide ongoing supervision to other study physicians to prevent therapeutic drift. All study psychiatrists will be trained in providing Medical Management and refresher training sessions will be provided every 6 months. As director of Columbia's Substance Treatment and Research Service, [name] has extensive experience conducting and supervising Medical Management and other similar medication adherence focused psychosocial intervention models.

**Study Visits:** Study visits will occur daily for the first 4 days of the study period. During the second week, patients will be asked to attend 3 study visits. During the remainder of the 8-week study period, study visits will occur twice weekly. There will be one visit during the taper week (week 9). There will be final post-taper visit after study medication is discontinued (week 10). One visit per week will be with the research psychiatrist. Participants will receive \$10 per visit for transportation expenses.

You can upload charts or diagrams if any  
table 1.medication dosing schedule.pdf

## **Criteria for Early Discontinuation**

### Criteria for Early Discontinuation

Drop-out criteria during the screening and study period include:

1. Development of serious psychiatric symptoms as indicated by a CGI improvement score of 6 (much worse than baseline) or greater for 2 consecutive weeks
2. Development of evidence of moderate-to-severe alcohol withdrawal (CIWA-Ar > 13) indicating a need for inpatient detoxification treatment
3. If the participant's continued alcohol use, even if improved from baseline, places him/her at risk for self-destructive behavior or other harm as indicated by a CGI improvement score of 6 (much worse than baseline) or greater for 2 consecutive weeks
4. If the participant becomes pregnant

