#### Describe procedures for minimizing risks

Participants are carefully screened for psychiatric risk prior to admission, so we anticipate the risk of clinically-significant psychological deterioration during participation to be low. The exclusion criteria are designed to minimize the medical and psychiatric risks to participants as discussed above, including risks of adverse events and side effects. All patients will be informed of the possible side effects and risks through extensive discussions with the research psychiatrist during the consent process.

Alcohol withdrawal will be assessed at each study visit using the Clinical Institute Withdrawal Alcohol (CIWA-AR). Anxiety and drinking will be assessed weekly.

Participants will provide a blood sample during screening; they will be warned that blood drawing may cause slight discomfort at the site of needle entry and may result in a small bruise.

Patients are informed prior to study entry that they can refuse to answer any questions and that they can request to stop at any time. If a participant becomes agitated during any of the interviews or assessments, he or she will be provided with therapeutic assistance.

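### The withdrawal drop-out cut-off is printed as CIWA-Ar > 13 in the discontinuation list but as ≥ 13 in Study Procedures; the two rules differ at a score of exactly 13.

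*Protocol*

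**What the plan says.** Three places in the protocol bear on this threshold.

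- **Criteria for Early Discontinuation, criterion 2** (the removal list): "Development of evidence of moderate-to-severe alcohol withdrawal (CIWA-Ar > 13) indicating a need for inpatient detoxification treatment". The list opens with "Drop-out criteria during the screening and study period include", so it covers screening as well as treatment and is not stated to be exhaustive.
- **Study Procedures, Study Participants paragraph:** after describing the gabapentin pilot, the text concludes "suggesting that a CIWA-Ar eligibility and drop-out threshold", with ≥ 13 printed directly after those words, and says that this threshold together with careful monitoring will protect participants.
- **Inclusion/Exclusion Criteria, exclusion 3:** "Evidence of moderate-to-severe alcohol withdrawal (CIWA-Ar $\geq 13". This is the same severity label as in criterion 2, set at ≥ 13.

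On how the score is used, the section on minimizing risks states: "Alcohol withdrawal will be assessed at each study visit using the Clinical Institute Withdrawal Alcohol (CIWA-AR". Study Procedures adds: "During the first two weeks of the study participants will be monitored frequently for the development of severe alcohol withdrawal symptoms". The SAP does not mention a CIWA-Ar cut-off.

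**The concern.** Criterion 2 is the withdrawal safety rule for outpatients who are still drinking at entry and are being asked to stop. Study Procedures justifies the trial's handling of withdrawal risk by a drop-out threshold of ≥ 13, yet the list that staff would consult when deciding on removal prints > 13. This is not a contrast between an entry rule and a removal rule, because the Study Procedures sentence names drop-out explicitly.

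At stake is what happens to a participant who scores exactly 13. One part of the protocol says the threshold has been reached and another says it has not. Only one visit per week is with the research psychiatrist, while CIWA-Ar is taken at every visit, so it is a fair inference that the printed number carries more weight at the other visits.

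**Working it through.** **The two rules as sets** (whole-number scores assumed)

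| CIWA-Ar score | Study Procedures (≥ 13) | Discontinuation list (> 13) |
|---|---|---|
| 12 or below | not flagged | not flagged |
| 13 | flagged | not flagged |
| 14 or above | flagged | flagged |

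The set {score ≥ 13} minus the set {score > 13} is {13}. The rules disagree at that value only.

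**Which version the rest of the text supports.** The ≥ 13 form appears four times: once in exclusion 3, and three times in the Study Participants paragraph (exclusion threshold, gabapentin pilot cut-off, joint eligibility and drop-out threshold). The > 13 form appears once, in criterion 2. Because the discontinuation list also covers screening, a 13 at screening is excluded under exclusion 3 without meeting the number in criterion 2.

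**What the pilot can say.** Study Procedures reports of the gabapentin pilot that "there were no serious adverse events and no participants were removed from the trial due to the development of alcohol withdrawal". With no removals for withdrawal, the pilot cannot distinguish a drop-out cut-off of 13 from one of 14. It shows neither that > 13 is unsafe nor that ≥ 13 is needed.

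**How often the rule is applied** (visit schedule in Study Procedures)

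- Weeks 1–8: 4 (week 1) + 3 (week 2) + 2 × 6 (weeks 3–8) = 19 visits per participant. This reproduces the 19 given in Compensation and/or Reimbursement.
- First two weeks: 4 + 3 = 7 visits.
- For 20 participants: at most 20 × 19 = 380 readings, of which 20 × 7 = 140 fall in the first two weeks.
- Adding the single visits in weeks 9 and 10: 19 + 2 = 21 visits, or at most 20 × 21 = 420 readings.

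These are counts of occasions on which the rule is applied. They are not counts of discordant readings.

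**Time to the next scheduled reading if a 13 is not flagged**

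- Between the first four visits: 1 day ("Study visits will occur daily for the first 4 days of the study period").
- After the fourth visit: at least 8 − 4 = 4 days, if the visits fall on days 1–4 and week 2 starts on day 8.
- Within week 2: about 7/3 = 2.3 days.
- Weeks 3–8: about 7/2 = 3.5 days.

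The last two assume even spacing; the documents do not give the visit days. The gap after day 4 is the longest of these and falls inside the two weeks that the protocol singles out for frequent monitoring.

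**The case against.** The strongest objection is that the mismatch may not exist in the source. It rests on one missing stroke under a > sign in text read from a PDF by a program. The same reading kept ≥ in all four other places, which weakens the objection but does not exclude it. It stands as a condition on the finding.

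Second, the Study Procedures sentence is rationale, while the operative removal list is elsewhere; and an entry cut-off may properly differ from a removal cut-off, so exclusion 3 alone does not contradict criterion 2. Both points are fair. But the rationale sentence states the drop-out threshold by name, and a protocol should not justify one threshold and list another.

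Third, criterion 2 is not a bare score rule. It carries a clause about the need for inpatient detoxification, and the list is open-ended. A participant scoring 13 who clinically needs detoxification can still be removed, and one scoring 14 is not removed automatically. This stands and is the main reason the effect is small. It does not say which number should prompt the clinical judgement.

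Fourth, no consequence is demonstrated: there is no evidence that > 13 is unsafe, no known frequency of 13s, and no effect on the analysis. That is correct, and it limits the severity. The inconsistency remains.

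**Conclusion.** The concern holds, as a minor internal inconsistency in a safety threshold. In the text supplied, the drop-out cut-off is > 13 in the discontinuation list and ≥ 13 in Study Procedures, and nothing in the protocol or SAP reconciles them. The disagreement is confined to a score of exactly 13.

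The conclusion assumes whole-number scoring and that the source PDF prints > 13; confidence is medium because the second could not be confirmed. No claim is made about how often a 13 will occur, about the relative safety of the two cut-offs, or about any effect on the outcomes, sample size or SAP.

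**What to change.** Check criterion 2 in the source PDF for a lost underline. If it prints ≥ 13, nothing needs changing. If it prints > 13, amend criterion 2 to CIWA-Ar ≥ 13 so that it agrees with exclusion 3 and Study Procedures, keeping the clinical-need clause. If the investigators do intend > 13 for drop-out, correct the joint threshold in Study Procedures instead, so that eligibility (≥ 13) and drop-out (> 13) are stated separately.

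Either route is a one-symbol or one-sentence amendment with no added visits, procedures or analyses. The only downside of moving criterion 2 to ≥ 13 is that a participant scoring exactly 13 could be removed, still subject to the clinical-need clause.

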## **Blood and other Biological Samples**

Please create or insert a table describing the proposed collection of blood or other biological specimens

Approximately 20 ml of blood (4 teaspoons) will be drawn at the time of baseline assessment for routine analyses including complete blood count, electrolytes, liver function tests, and blood pregnancy test for women. They may be repeated during the study if clinically indicated.

***Urinalysis:*** Laboratory urinalysis (glucose, protein, ketones, pH, specific gravity, microscopic analysis) will be performed during the screening process.

***Urine Toxicology:*** Urine samples for toxicology will be collected under directly observed conditions during screening and study weeks 4 and 8 to detect any non-alcohol substance use.

## Assessment Instruments

Create a table or give a brief description of the instruments that will be used for assessment

